6.14. DATE AND SOURCE DOCUMENTS

6.14.1. MEDICAL HISTORY

The data will be collected from the electronic medical record (Jimena IV) and, where appropriate, the paper medical record. Also part of the medical record are the records of the ICCA applications.

6.14.2. WHAT IS CONSIDERED A SOURCE DOCUMENT IN THIS ESSAY

Source Data: All information in original documents and certified copies of original records of clinical results, observations, or other activities of a clinical trial necessary for the reconstruction and evaluation of the trial. The source data will be included in the source documents (original records or certified copies).

Source documents: original documents, data and records (e.g., patient records, medical or consultation records, laboratory notes, memoranda, records, data recorded on automated instruments, certified copies or transcripts after verification, microfiche, photographic negatives, microfilm or magnetic media, radiographs, subject files and pharmacy records in laboratories and in medical-technical departments involved in the clinical trial).

Patients must have allowed their medical history to be read in writing by staff authorized by the sponsor and regulatory authorities. This information is included in the informed consent.

6.14.3 DIRECT ACCESS TO SOURCE DATA/DOCUMENTS

The Promoter shall sign appropriate agreements to appoint a monitor who will supervise this study and shall periodically contact the centre, including the management of visits to the centre. The researcher agrees to allow the monitor direct access to all relevant documents and to devote his or her and his or her staff's time to the monitor to comment on the results and any matters of interest.

6.14.4 QUALITY CONTROL AND ASSURANCE

In order to ensure the quality of the data, the sponsor shall:

- Instructions and quality training will be provided to the research staff before the start of the study. Training topics include, but are not limited to: GCP certificates, AA reports, study details and procedures, study documentation, informed consent, and patient recruitment.
- Perform regular monitoring in accordance with the International Conference on Harmonization (ICH) for Good Clinical Practice (GCP). The data will be evaluated for adherence to protocol and accuracy relative to the source documents. The monitors will verify that the clinical trial is carried out, that the data is generated, documented and reported in compliance with the protocol, good clinical practice and any applicable local regulatory requirements.

Direct access to the data will be granted to the principal investigators, monitors, members of the evaluating CEIm and the AEMPS, as well as to the authorities that are necessary, in order to allow monitoring and surveillance related to the study, audits and inspections. At each center, they will be able to review the study records and compare them directly with the source documents, they could discuss how to conduct the study with the researcher, and verify that the facilities remain acceptable. Audit reports shall be treated confidentially

7. ETHICAL AND LEGAL ASPECTS AND OBTAINING INFORMED CONSENT

This study has been designed in accordance with the general ethical principles set out in the Declaration of Helsinki (64th General Assembly, Fortaleza, Brazil, October 2013). The researchers will carry out the study in accordance with the Good Clinical Practices (PCB), described in harmonized Tripartite Guidelines of the ICH of Good Clinical Practices and the Document of instructions of the Spanish Agency of Medicines and Health Products for the conduct of clinical trials in Spain (Version 9 of July 27, 2018).

The researcher will prepare the documents to request evaluation by the Ethics Committee of Research with medicines of the Health Area of Salamanca, and will respond, where appropriate, to the request for clarifications. Approval of the CEIm will be obtained before the start of the study. The study will be notified to the Spanish Agency for Medicines and Health Products (AEMPS).

The researcher will facilitate the performance of monitoring visits and audits by the Promoter, reviews of the CEIm, and regulatory inspection(s) if necessary, providing direct access to the facilities where the study was carried out, to the source documents, to the CRDs, and to all other study documents.

The investigator shall obtain the informed consent of a patient or his/her legal representative before initiating any procedure related to the study, in accordance with the PCBs, as stipulated in the ICH guidelines. It will be recorded in the patient's source documents (medical history) that informed consent has been obtained prior to the patient's entry into the study. The original consent form, signed and dated by the patient and by the investigator will be kept in the study investigator's file. When the investigator proposes to the patient his inclusion in the study, he will inform him in depth about the objectives, possible risks and benefits of his participation, he will answer all the questions that the patient may ask, who will have time to decide his participation in the study. When the patient is legally incapacitated or is not in a position to sign the consent, his legal representative will do so, in accordance with the hospital's policy and the legislation in force in this matter. In the event that a family member signs the consent because the patient is not in a position to sign the consent, and is not legally incapacitated, consent will be requested as soon as possible, when he meets the appropriate conditions, to ratify the consent given by his family.

8. DATA PROTECTION AND CONFIDENTIALITY

REGULATION (EU) No 536/2014 requires that subject data be treated in accordance with Union data protection legislation. In Spain, Organic Law 3/2018, of December 5, on the Protection of Personal Data and guarantee of digital rights, complementary to Regulation (EU) 2016/679 of the European Parliament and of the Council, of April 27, 2016, on the protection of natural persons with regard to the processing of personal data and on the free movement of these data and repealing Directive 95/46/ CE. This legislation requires the application of high-level security measures in the handling of health data, so that the distribution of the media is carried out by encrypting said data or using another mechanism that guarantees that said information is not accessible or manipulated during its transport.

Study data will be protected and confidentiality will be maintained in accordance with current legislation. Patients will be identified by a code and only the research team, qualified personnel in charge of monitoring, health authorities, or other authorized third parties may review the medical records of patients. The code used will not allow the identification of the subject, and will not include or collect identifying data such as the medical record number or similar assigned by the Administration, the name, surname, initials of the subject, the postal address or email address, the telephone number, the tax identification number, the fingerprint, THE DNA, a photograph, the social security number, ...

The collected data (CRD) will be stored encoded in a database hosted on causa's servers, under the supervision of the principal investigator. Causa servers are subject to security controls and regulations in accordance with hospital policy and applicable data protection regulations.

The researcher will ensure that the records and documents of the study as original signed consents, any type of source document (hospital records, medical records, ultrasound records of *the procedure* datos de laboratorio...) y CRD, will be kept for the time required by current legislation. Likewise, you agree to comply with the procedures of conservation of documents / records by signing the protocol.

9. PROTOCOL CHANGES

If a modification to the test protocol is necessary, the modification or a new version of the trial protocol (modified protocol) will be notified to the CEIm of the Salamanca Health Area, to be approved by it before its application.

10. ANALYSIS AND COMMUNICATION OF RESULTS

The analysis of the data will be carried out by the research team and will be communicated in meetings and scientific articles in peer-reviewed journals. Regardless of the results of the study, the sponsor agrees to present them to the medical community through scientific publications, congresses or other means.

ANNEX I. - ANESTHETIC PROTOCOL

- Standard patient monitoring in the operating room.
- Intravenous sedoanalgesia for puncture. We will not use, and in any case we will avoid long-acting benzodiazepines (if essential Midazolam 0.5-1mg).
- Ultrasound puncture with patient in supine position, without moving him in bed.
- Anesthetics to use:
 - -Group R: Ropivacaine 0.375% (25 cc): will be administered: 20 cc for PENG and 5 cc for BNFCL
 - -Group L: Levobupivacaine 0.25% (25 cc): 20 cc will be administered for PENG and 5 cc for BNFCL.
- Assess latency: explore until pain disappears on passive mobilization. maximum 10 minutes.
- Performance of the subarachnoid block in a sitting position on the operating table. Dose: 0.5% hyperbaric bupivacaine (5 mg) + 10 µg of Fentanyl.
- Record the required surgical variables on the collection sheet.

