2.2.2 LEVOBUPIVACAINE

Levobupivacaine is a long-acting local amide-type anesthetic with both analgesic and anesthetic effects, approved in our country since November 2013.

It works by blocking nerve conduction in sensory and motor nerves largely due to interaction with cell membrane voltage-gated sodium channels, but also blocks potassium and calcium channels. In addition, Levobupivacaine interferes with impulse transmission and conduction in other tissues where effects on the cardiovascular and central nervous systems are the most important for the occurrence of clinical adverse reactions. The dose of Levobupivacaine is considered equipotente with bupivacaine.

Levobupivacaine is indicated in adults in Major Surgical Anesthesia (e.g. epidural, intrathecal, peripheral nerve block) and Minor (e.g. local infiltration, peribulbar block in ophthalmic surgery) and for the treatment of pain (in continuous epidural perfusion, single or multiple bolus epidural administration for the treatment of pain, especially post-surgical pain). In analgesia (e.g. epidural administration for the treatment of pain) the lowest concentrations and doses are recommended. When deep or prolonged anaesthesia with complete motor block (e.g. epidural or peribulbar block) is required, the highest concentrations may be used. Careful aspiration is recommended before and during injection to avoid intravascular injection.

The maximum dose should be determined by assessing the size and physical condition of the patient, along with the concentration of the drug and the area and route of administration. There is an individual variation in the onset and duration of the block. Experience gained in clinical trials shows that sensory block suitable for surgery occurs within 10-15 minutes after epidural administration, with a regression time in the range of 6-9 hours. In the treatment of post-surgical pain, the dose administered during surgery should be taken into account. When used for regional major nerve block, the lowest effective dose of local anesthetic should be used to avoid high plasma levels and serious adverse reactions.

There are no relevant data on Levobupivacaine in patients with hepatic impairment, although it is metabolised in the liver, and should be used with caution in patients with liver disease or reduced hepatic blood flow. Levobupivacaine is extensively metabolized without detecting unchanged Levobupivacaine in urine or feces.

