3. HYPOTHESES AND OBJECTIVES

3.1. HYPOTHESIS:

Levobupivacaine has advantages over Ropivacaine in the combined blockade (PENG - pericapsular nerve group- and the femoral lateral cutaneous nerve -BNFCL-) in hip fractures of the elderly, since a better analgesic control, similar latency period, and a longer analgesic duration are obtained.

3.2. OBJECTIVES:

3.2.1. MAIN:

- To compare the analgesic efficacy of both local anaesthetics in the regional blockade of hip fracture surgery.

3.2.2. SECONDARY:

- To describe the behavior of this combined technique in hip fractures, establishing latency of onset and duration of analgesia.
- Describe the side effects derived from the described combined technique. To validate in our population, especially in patients with cognitive impairment, the usefulness of the analgesic scales chosen.

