6.7. MEASUREMENTS

- Demographic variables: age, sex, weight, height, comorbidity (ASA grade).
- Variables related to the injury: subcapital fracture, pectrochanteric, subpectrochanteric or others.
- Variables related to the type of surgery: partial hip arthroplasty, endomedullary nailing or others. Duration of surgery.
- Variables related to the response:
 - Latency: evaluated by analgesic scales up to 10 minutes.
 - Analgesic scales: EVN, Algoplus and PAINAD at rest and in activity. They will be carried out upon the patient's arrival at the operating room, continuous until 10 minutes after the nerve block, in the sedation for the subarachnoid block, when they are discharged from the URPA, and at 6, 12, 24 h after the realization of the block, and end of effect after the realization of the block.
 - Need and rescue drugs: rescue analgesia will be scheduled for the hospitalization floor, in case it is necessary. The need, drug and time of administration regarding the realization of the blockade will be collected (Annex II).

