6.8. ANESTHETIC PROTOCOL

- After giving informed consent to the patient or his guardian, the patient is monitored according to the usual standard (SEDAR Protocol, which includes ECG, TA, SatpO2).
- The ultrasound-guided block at the femoral level (PENG) is performed in the patient's transfer bed or table, depositing 20 cc of local anesthetic, with a 50-80 mm needle (depending on the anatomical characteristics) and a low-frequency probe. Next, a 50 mm needle and the high-frequency ultrasound probe will be used to block the NFCL by depositing 5 cc

of the same anesthetic, always without exceeding the maximum recommended dose for each drug. (See Annex I).

- Latency in the establishment of analgesia in the affected territory is explored, as well as an assessment of pain (Numerical Visual Scale and Algoplus).
- We proceed to the realization of the intradural spinal anesthesia, assessing again the pain that manifests. Subarachnoid blockade will always be performed with the same dose: 5 mg of Bupivacaine 0.5% hyperbaric with 10 µg of Fentanyl.
- After the surgical intervention, he will be transferred to the URPA (Post-Anesthetic Recovery Unit) and, subsequently, to the hospitalization floor when his situation allows it. At all times the constants, the analgesic variables and the treatments that you have needed will be recorded. (See Annex II).

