6.10. STATISTICAL ANALYSIS

A descriptive analysis of the variables collected will be carried out. Non-categorical ones shall be expressed as median +/- IQR (interquartile amplitude). Categorical variables shall be expressed as percentages or frequencies.

After performing the relevant normality tests (Kolmogorov-Smirnov or Shapiro-Wilk), the sample differences will be determined by t-Student or Mann-Whitney U tests. In the comparison of pain scales we will use the analysis of variance (ANOVA or Kruskal-Wallis).

The comparative analysis of the categorical variables will be carried out by means of Chi-square tests with cross tables.

The control of the possible intermediate and confusing variables will be carried out by means of Multiple Linear Regression Analysis.

The significance level will be, by default, 5% (p<0.05).

All calculations will be carried out with the statistical program SPSS[®] 25.0 for Mac.

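### The hypothesis claims similar latency, but the plan tests only for a difference and has no rule for patients without onset when observation stops at 10 minutes

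*Combined protocol and SAP*

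**What the plan says.** - **Hypothesis (3.1).** Levobupivacaine is expected to be better "since a better analgesic control, similar latency period, and a longer analgesic duration are obtained". No margin says what counts as similar.
- **Objective and endpoint (3.2.2, 1.14).** Latency is a secondary objective of a descriptive kind and the first secondary variable listed.
- **Measurement (6.7, 6.8, Annex I).** Section 6.7: "Latency: evaluated by analgesic scales up to 10 minutes". Section 6.8 explores latency of analgesia in the affected territory, "as well as an assessment of pain (Numerical Visual Scale and Algoplus"), with no time limit. Annex I: "explore until pain disappears on passive mobilization. maximum 10 minutes". Only Annex I names an event. In both 6.8 and Annex I the spinal block comes next.
- **Recording (Annex III).** There is one latency field, with no unit, no event and no code for onset not reached.
- **Analysis (6.10).** After normality tests, "the sample differences will be determined by t-Student or Mann-Whitney U tests", at the 5% level. There is no equivalence test, interval rule or method for censored times.

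**The concern.** Two gaps meet in the same variable.

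First, similarity is a claim that the arms differ by no more than some amount. A difference test cannot establish it: a p-value above 0.05 may mean only that the estimate is imprecise. One of the three parts of the hypothesis therefore has no analysis that could support it.

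Second, latency is right-censored. A patient still in pain at 10 minutes has a latency longer than 10, and the spinal block then prevents any later reading. The analyst must score that patient as 10, leave the field empty or drop the patient, and the plan does not say which. These choices can lead to opposite conclusions from the same data.

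Section 2.3 makes latency matter in practice, because a short latency helps surgery to start.

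**Working it through.** **Inputs.** From 6.9: 54 per arm with 10% losses, so 54 × 0.9 = 48.6, taken as 49 evaluable per arm. From 6.10: alpha 5%, read here as two-sided because sidedness is not stated. From 6.7 and Annex I: the 10-minute limit. The documents give no mean, SD or margin for latency, so these are assumed below. There is no latency figure of the plan's own to reproduce, since the 108 patients were sized on duration of block.

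**Step 1. What a non-significant result would show, ignoring the cap.**
SE = SD × √(2/49). The 95% CI half-width is 1.96 × SE. P(non-significant) = 1 − Φ(δ/SE − 1.96) − Φ(−δ/SE − 1.96).

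| Assumed SD | SE | CI half-width | True δ = 2 min: δ/SE, P(n.s.) | True δ = 1 min: δ/SE, P(n.s.) |
|---|---|---|---|---|
| 4 min | 0.808 | 1.58 min | 2.475, 30% | 1.237, 76% |
| 5 min | 1.010 | 1.98 min | 1.980, 49% | 0.990, 83% |

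Non-significance is thus common even when a real difference exists.

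**Step 2. What the cap does under each way of handling patients without onset.**
Latencies are drawn from gamma distributions with shape (mean/SD)² and scale SD²/mean, 49 per arm, and compared by two-sided Mann-Whitney at 5%. The share without onset is P(latency > 10).

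| Assumed means (SD) | No onset by 10 min | Power, no cap | Scored as 10 | Dropped |
|---|---|---|---|---|
| 5 vs 7 (3) | 7%, 15% | 95% | 95% | 93% |
| 10 vs 13 (4) | 45%, 76% | 96% | 95% | 40% |
| 13 vs 16 (4) | 76%, 95% | 96% | 80% | 4% |

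Powers are simulated, so they carry an error of about one percentage point. In the middle row the true 3-minute difference in means is estimated as about 1.2 minutes if non-reachers are scored as 10, and about 1.1 minutes if they are dropped.

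**Step 3. What a similarity claim would need.**
To have 80% power that the 95% CI lies inside ±margin when the arms are truly equal, n per arm = 2 × [SD × (1.960 + 1.282)/margin]², again ignoring the cap.
- Margin 2 min: 85 (SD 4) or 132 (SD 5).
- Margin 3 min: 38 (SD 4) or 59 (SD 5).

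Whether 49 per arm is enough depends on a margin and an SD that the plan does not give.

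**The case against.** A reader might infer that the plan will declare the latencies similar from p > 0.05, and that the cap makes this result certain. The documents support neither.

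- **No such decision rule is written.** Section 6.10 speaks of differences only, and the latency objective is to describe. Reading non-significance as similarity is a risk that the hypothesis invites, not a planned inference.
- **Truncation alone need not hide a difference.** Scoring non-reachers as 10 shrinks the spread as well as the difference, and the rank test keeps nearly all its power at 10 vs 13 minutes (96% to 95%). The serious loss comes from dropping them, or when most patients in both arms exceed 10 minutes. The plan does not say they will be dropped.
- **The cap may rarely bind.** The only onset time in the documents is in 2.2.2: "sensory block suitable for surgery occurs within 10-15 minutes after epidural administration". That is another route and another end-effect from pain relief on passive mobilization after a peripheral block. It cannot show that many patients here will lack onset.
- **The latency descriptions partly agree.** Section 6.7 asks for the scales in activity and continuously to 10 minutes, which fits passive mobilization in Annex I. Section 6.8 lists two scales alongside latency, not as its definition. What remains is that no threshold score or assessment interval is given, and that 6.8 leaves out PAINAD.
- **Sedation is a side issue.** Annex I provides "Intravenous sedoanalgesia for puncture" in both arms. It may add noise to the scores, and Annex III has no row for it, but that is a small recording gap.

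These points limit the size of the problem. They do not supply a margin, an interval rule or a rule for patients without onset.

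**Conclusion.** The point stands in this form: the planned tests cannot support the similarity part of 3.1, and the result for latency can turn on a handling rule that the plan leaves open. That rule costs almost nothing if onset is early (95% vs 93% power at 5 vs 7 minutes). It decides the result if onset is near or beyond 10 minutes (95% vs 40%, or 80% vs 4%). Even where power is kept, the estimated difference in means is too small. All means and SDs are assumptions. That observation is cut at 10 minutes with no rule for non-reachers, and that no margin is stated, comes directly from the text. Latency is secondary, so the primary comparison of block duration is unaffected. The plan should be corrected on this point, but it does not put the trial in doubt.

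**What to change.** 1. **6.10:** keep every patient without onset in the analysis, either as censored at 10 minutes in a time-to-onset analysis or as ties at 10 in a rank test. Report the proportion pain-free at 10 minutes per arm, with a 95% CI for the difference.
2. **3.1:** drop the word similar and report latency descriptively, or allow the claim only if the 95% CI lies inside a margin fixed before data are seen. Never base it on p > 0.05. Set the margin on a quantity that can be observed within 10 minutes, such as the proportion pain-free.
3. **Annex III:** give the latency field a unit and a code for onset not reached by 10 minutes. A row for the sedoanalgesia given is an optional small addition.
4. **6.7, 6.8 and Annex I:** reconcile the descriptions to one event, stating the scale, the threshold, rest or movement, and the assessment interval.

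The 10-minute clinical limit is not touched, and no extra patients or procedures are needed. The cost is some wording, one form code and a harder similarity claim. With 49 per arm and proportions near 50%, the 95% CI half-width for the difference is 1.96 × √(2 × 0.25/49) = 0.198, about 20 percentage points, so only a wide margin could be met.
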